14.4 Appendix 4 Cough Visual Analogue Scale

Please put a cross on the line to indicate the severity of your cough in the past 2 weeks.

14.5 Appendix 5 Protocol Amendments

Protocol Amendment and Date	Section and Summary of Changes	Reason
Version 5 27Apr2023	
 Section 4.1.1 – Changed diagnosis to within last 3 years, removed FVC upper limit, updated DLCO upper limit to 80, and allowed historical treatment of previous anti-fibrotic therapy to within 2 months of the Baseline bronchoscopy Section 7.2 – Update PK sample to 5 minutes post-dose instead of 30 minutes 	
 Allows for a broader subject population More likely to measure LTI-03 level above lower limit of detection
Version 4 04Jan2023	
 Administrative Changes Section 6.1.4 – Added discontinuation for decrease from Baseline in FEV1 of 15% Section 6.7 – Added additional post-dose and as needed spirometry Section 8.8 – Added unrelated similar SAE or severe or higher AE in > 2 subjects' criterion to stopping rules 	
 Administrative changes Added safety measure Additional monitoring for potential airway obstruction Additional safety measure
Version 3 06Oct2022	
 Section 1.1.1, 1.2, and 1.3 – Update language to include rationale for placebo and SOC medication Section 2.2.2 – Added Leicester Cough Questionnaire and Cough Visual Analogue Scale to safety endpoints 	
 Provides rationale for SOC medication restriction during dosing of LTI-03 Data to be summarized as endpoints

	
 • Section 3 – Describe safety reviews • Section 4.12 – Update exclusion criteria to match investigator's brochure • Section 5.6 – Add language to allow investigators to use SOC medications • Section 6.0 and 6.9 – Update to provide both BAL and BA can be completed. • Section 8.8 – Update to clarify stopping rules and describe protocol amendment requirements • Section 9.3 – Remove analysis populations • Section 9.4.7 Added data analysis description after Cohort 1 • Administrative changes 	
 • Update to provide details regarding the safety review meetings to occur prior to dose escalation • Updated to match investigator's brochure special populations • Provides flexibility for investigators to allow SOC medications if necessary • Allows for flexibility for investigational site to use SOC procedures • Provide clear details when stopping rules would apply • Details to be provided in the SAP • Allows for analysis of Cohort 1 • Administrative changes
Version 2 17Jun2022	
 • Section 3.0 and 6.9 - Addition of bronchoabsorption • Section 4.1 - Addition of serum to pregnancy test • Section 7.1 - Allowing rescreening of subjects • Section 7 – Administrative changes 	
 • Allows for flexibility for investigational site to use SOC procedures • Allows for flexibility for investigational site to use SOC procedures based on local regulations • Subjects can be re-screened once • Administrative changes

## DOCUMENT HISTORY

Version	Date	Changes
Version 1.0	01Sep2023	Initial version
Version 2.0	10Oct2024	Protocol deviation severity and significant status defined, 15% baseline FEV1 replaced by 15% decrease from Baseline FEV1, rule for BLQ value in biomarkers data

## List of Abbreviations

AE	Adverse Event
AEC2	Alveolar Epithelial Type 2 Cells
ALP	Alkaline Phosphatase
ALT	Alanine Aminotransferase
aPTT	activated Partial Thromboplastin Time
AST	Aspartate Aminotransferase
ATS	American Thoracic Society
AV	Atrioventricular
BA	Bronchoabsorption
BAL	Bronchoalveolar Lavage
BALF	Bronchoalveolar Lavage Fluid
BID	Twice daily
BUN	Blood Urea Nitrogen
CK	Creatine Kinase
CRF	Case Report Form
CRO	Contract Research Organization
CRP	C-reactive protein
CSD	Caveolin-1 Scaffolding Domain
CTCAE	Common Terminology Criteria for Adverse Events
CTMS	Clinical Trial Management System
DLCO	Diffusion Capacity of the Lungs for Carbon Monoxide
ECG	Electrocardiogram
ECM	Extracellular Matrix
EOS	End of Study
ERS	European Respiratory Society
EU	European Union
FEV 1	Forced Expiratory Volume 1
FLF	Fibrotic Lung Fibroblast
FN	Fibronectin
FOCBP	Female of Childbearing Potential
FVC	Forced Vital Capacity

GGT	Gamma Glutamyltransferase
HDL-C	High Density Lipoprotein Cholesterol
Hgb	Hemoglobin
HR	Heart Rate
HRCT	High-resolution Computed Tomography
IB	Investigator's Brochure
ICH	International Council for Harmonization
ILD	Interstitial Lung Disease
IPF	Idiopathic Pulmonary Fibrosis
IVRS	Interactive Voice Response System
LCQ	Leicester Cough Questionnaire
LDH	Lactate Dehydrogenase
LDL-C	Low Density Lipoprotein Cholesterol
MCH	Mean Corpuscular Hemoglobin
MCHC	Mean Corpuscular Hemoglobin Concentration
MCV	Mean Corpuscular Volume
MedDRA	Medical Dictionary for Regulatory Activities
NCI	National Cancer Institute
PD	Pharmacodynamic
PR	P to R interval
PK	Pharmacokinetic
PT	Prothrombin Time
QD	Once Daily
QRS	QRS wave
QT	Q to T interval
QTcF	QT interval corrected for heart rate calculated using Fridericia's formula
RBC	Red blood cell
RDW	Red cell Distribution Width
RR	R to R interval for ECGs
SAE	Serious Adverse Event
SAP	Statistical Analysis Plan
SAS	Statistical Analysis System

SOA	Schedule of Assessments
TEAE	Treatment-Emergent Adverse Event
VAS	Visual Analogue Scale
WBC	White Blood Cell
WHODD	World Health Organization Drug Dictionary

## 1. Introduction

This Statistical Analysis Plan (SAP) defines the statistical methods and data presentations for the Lung Therapeutics, Inc. protocol LTI-03-1002 study entitled “A Randomized, Double-Blind, Placebo-Controlled, Phase 1b, Dose Escalation, Safety, Tolerability and Pharmacodynamic Biomarker Study of Caveolin-1-Scaffolding-Protein-Derived Peptide (LTI-03) in Recently Diagnosed, Treatment Naïve Subjects with Idiopathic Pulmonary Fibrosis”.

This SAP covers all specified analysis for the final study reports based on the study protocol Version 5.0 dated 04 May2023.

## 2. Objectives

### 2.1. Primary Objective

- To determine the safety and tolerability of inhaled LTI-03 in subjects diagnosed with IPF within 3 years of Screening.

### 2.2. Exploratory Objectives

- To assess the plasma pharmacokinetic (PK) of inhaled LTI-03 after the first dose and at steady state in subjects with IPF diagnosed within 3 years of Screening.
- To evaluate the pharmacodynamic (PD) biomarkers of inhaled LTI-03 in subjects diagnosed with IPF within 3 years of Screening.

## 3. Investigational Plan

### 3.1. Overall Study Design and Plan

This is a randomized, double-blind, placebo-controlled, multi-center, dose escalation, safety and tolerability study of LTI-03 or placebo administered by inhalation in subjects with IPF without prior treatment with anti-fibrotic agents within 2 months of the Baseline bronchoscopy. An IPF diagnosis will be confirmed by high-resolution computed tomography (HRCT) of chest or lung biopsy within 3 years prior to Screening. The study will contain 2 dose cohorts which will run sequentially. Subjects in the first, low-dose cohort (Cohort 1) will receive 2.5 mg of study drug (LTI-03 or placebo), administered twice daily approximately 10-12 hours apart (5 mg per day). If the 5 mg per day dose is well tolerated, a second, high-dose cohort (Cohort 2) will receive 5 mg of study drug (LTI-03 or placebo), administered twice daily approximately 10-12 hours apart (10 mg per day).

Eligible subjects will be randomized in a 3:1 ratio to either LTI-03 or placebo. Each cohort will have 9 subjects randomized to LTI-03 and 3 subjects randomized to placebo. Safety data will be reviewed on an ongoing basis by the Sponsor's medical officer and the Contract Research Organization (CRO)'s medical monitor. A review of safety data including but not limited to adverse events, laboratory assessments, vital signs, and spirometry will be conducted after all 12 subjects from Cohort 1 have completed Day 14 assessments. Enrollment in the second cohort will not begin until the Cohort 1 safety data has been reviewed and a dose decision made. A lower dose cohort may be added (2.5 mg administered once daily) or additional subjects (up to 12 subjects) may be added to the low-dose cohort (2.5 mg administered twice daily) if doses of

5 mg twice daily (10 mg per day) are not tolerated. In total, a maximum of approximately 24 subjects will be randomized in the study.

The Treatment Period will be 14 days, with subjects self-administering the study drug using the provided commercially available dry powder inhaler. All subjects will be trained on the proper methods of inhaler use and will have access to site personnel trained to assist subjects remotely if questions arise. Retraining may occur on Day 1 and 7, if required. During the Treatment Period, there will be on-site visits on Day 1, Day 7, and Day 14 and study assessments will occur at the investigational site on these days. The first dose of study drug will be administered at the investigational site and subjects will be monitored for at least 1 hour after dosing.

Screening assessments may take place over no more than 21 days prior to the Treatment Period. Screening assessments will include but not be limited to a complete physical examination including vital signs, electrocardiogram (ECG), spirometry, safety laboratory parameters, medical history, and concomitant medications. A Baseline bronchoscopy will be performed during the Screening Period in subjects who meet the Screening criteria and will include bronchoalveolar lavage (BAL) and/or bronchoabsorption (BA), and deep bronchial brushings.

Treatment Period will include but not be limited to physical examinations with vital signs, ECG, spirometry, clinical laboratory assessments, adverse event (AE) assessment, Leicester cough questionnaire, cough visual analogue scale (VAS), and concomitant medications. Bronchoscopies with BAL and/or BA and deep bronchial brushings will also be performed on Day 14 approximately 2-3 hours after morning dosing.

Follow-up study assessments will be completed at Day 21 with all Day 14 assessments repeated except dosing, bronchoscopy, and blood collection for biomarkers and PK. Also, a complete physical examination will be replaced by a brief physical examination. The end of the study is defined as the date of the last visit of the last participant in the study.

## **3.2. Study Endpoints**

### **3.2.1. Primary Endpoint**

- Incidence of Treatment Emergent Adverse Events (TEAE).

### **3.2.2 Other Safety Endpoints**

- Other safety endpoints include:
  - Physical examination findings
  - Vital signs
  - ECG
  - Clinical laboratory measurements
  - Spirometry
  - Leicester Cough Questionnaire (LCQ)
  - Cough VAS

### **3.2.3. Exploratory Endpoints**

- To determine the plasma peak and trough concentration of LTI-03 after the first dose and at steady state.

- Change from baseline over time for biomarkers related to the pathophysiology of IPF.

### 3.3. Treatments

LTI-03 and matching placebo will be provided as inhalation powders for oral inhalation use. LTI-03, as an excipient-free, micronized dry powder, will be placed into white opaque hypromellose two-piece capsules. The placebo will be micronized lactose powder that is placed into white opaque hypromellose two-piece capsules and will be identical in appearance to LTI-03. Individual capsules containing 2.5 mg of study drug (LTI-03 or placebo) will not be labelled.

### 3.4. Dose Adjustment/Modifications

No dose adjustment is planned. A lower dose cohort may be added (2.5 mg administered once daily (QD)) or additional subjects may be added to the low-dose cohort (2.5 mg administered BID) if doses of 5 mg BID (10 mg per day) are not tolerated. If a lower dose cohort is added, the treatments will be appropriately described/updated and summarized in the TFLs.

## 4. General Statistical Considerations

This section presents general rules for the derivation and reporting of study data. If a subsequent section related to a specific derivation or analysis differs from this general guidance, the subsequent section takes precedence.

Continuous data will be presented using descriptive statistics (i.e. n, mean, standard deviation, median, minimum, and maximum). Categorical data will be presented using frequency counts and percentages in each category. For the summary statistics of all numerical variables (unless otherwise specified), minimum and maximum will be displayed to the same level of precision of the raw data. Mean and median will be displayed to one level of precision greater than the data collected. Standard deviation will be displayed to two levels of precision greater than the data collected.

When count data are presented, the percentage will be suppressed when the count is zero in order to draw attention to the non-zero counts. A row denoted “Missing” will be included in count tabulations where specified on the shells to account for missing values. The denominator for all percentages will be the number of subjects in that treatment group within the analysis set of interest, unless otherwise specified. Percentages will be presented to one decimal place except for the display of 100% frequency which will be displayed as ‘XX (100)’.

In general, all tables will be presented by treatment (active treatments, active treatment total, and pooled placebo). Subjects from all cohorts who took placebo will be combined to form a pooled placebo group for analyses. All study data will be presented in by-subject data listings.

“No data available for this report” will be presented when there are no data available to report.

The primary endpoint of the study is safety and no formal statistical hypotheses will be tested.

All descriptive statistical analyses will be performed using Statistical Analysis System (SAS) statistical software (version 9.4 or higher). Missing data will not be imputed unless otherwise stated.

#### **4.1. Baseline, End of Study and Study Day**

Unless otherwise specified, baseline will be defined as the last non-missing evaluation prior to the date and time that the first dose of treatment is taken. Baseline values for spirometry are the mean of the Day 1 pre-dose and the value collected during screening using the same spirometry equipment (see [Section 8.6](#)).

A participant will have completed the study if all visits are completed and the End of Study eCRF is marked as completed. The end of study date for each participant is defined as the date of the last visit as recorded on the End of Study eCRF.

Study day is defined in relation to the date of first dose of study drug (on Day 1). Therefore, when an assessment date is before the first dose:

Study day = assessment date - first dose date of study drug

and when an assessment is on or after the first dose:

Study day = assessment date - first dose date of study drug + 1

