7.1 Screening Period (Day -21 to Day -1)

During Screening, a unique study-assigned subject number will be assigned to each subject who signs the informed consent for the study. Once subjects are in Screening or are enrolled in the study, they will only be identified by the assigned identification number. A subject may be rescreened once, providing that additional written informed consent is obtained.

The reason(s) why a subject is not eligible for the study will be collected.

The following procedures and assessments will be performed during the Screening Period to confirm eligibility.

- Obtain written informed consent
- Record demographics and medical history
- *Record prior and concomitant medications taken within 30 days prior to first dose of study drug (Day 1)
- Obtain vital signs (blood pressure, heart rate, respiratory rate, body temperature, and hemoglobin oxygen saturation via pulse oximetry)
- *Perform a complete physical examination (including documentation of height and weight)
- Assess ability to use inhaler
- Single 12-lead ECG
- Perform spirometry with DLCO
- Collect blood sample for the following:
 - Hematology
 - Clinical chemistry
 - Coagulation
 - *Biomarker assessments
- Collect urine or serum sample for pregnancy test, if applicable
- Confirm eligibility according to inclusion/exclusion criteria.
- *Leicester Cough Questionnaire and Cough VAS prior to bronchoscopy

- *Adverse event assessment
- Baseline bronchoscopy with BAL and/or BA and deep bronchial brushings for biomarkers will be performed during the Screening Period in those subjects who have provided informed consent. Prior to bronchoscopy, the assessments with * in Section 7.1 will be performed.

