7.2 Treatment Period

7.2.1 Day 1

The first dose of study drug will be administered at the investigational site and subjects will be monitored for at least 1 hour after dosing. Study staff will provide retraining on inhaler use, if required.

Assessments and procedures performed prior to dosing include:

- Confirmation of eligibility
- Concomitant medication assessments
- Adverse event assessment
- Brief physical examination
- Vital signs
- Single 12-lead ECG
- Collect urine or serum sample for pregnancy test.
- Randomization
- Collect blood for the following:
 - Hematology
 - Clinical chemistry
 - PK (pre-dose)
- Leicester Cough Questionnaire and Cough VAS
- Spirometry
- Dispense study medication and inhaler kit and administer Study Drug

Assessments and procedures performed after dosing include:

- Adverse event assessment
- Vital signs
- Collection of blood sample for the PK at 5 minutes (+ 5 minutes) after dosing

- Spirometry at 30 minutes (\pm 10 minutes) and 1 hour (\pm 10 minutes) after dosing

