7.2.4 Days 8-13

Subjects will self-administer study drug at home and will be contacted on Day 10 (\pm 2 days) by study staff to check on compliance and for potential AEs.

7.2.5 Day 14

Subjects will return to the clinic on Day 14 (\pm 1 day) and the follow-up bronchoscopy will be performed. Subjects will be instructed to hold the morning administration of study drug until arrival at their clinical visit. Study staff will note the time of the dose and check on compliance. Follow-up bronchoscopy should occur approximately 2-3 hours after morning dosing. The second study drug dose will not be administered on Day 14.

All assessments and procedures will be performed prior to bronchoscopy.

Assessments and procedures performed before dosing during this visit include:

- Concomitant medication assessments
- Adverse event assessment
- Complete physical examination
- Vital signs
- Single 12-lead ECG
- Collect urine or serum sample for pregnancy test.
- Collect blood for the following:
 - Hematology
 - Clinical chemistry
 - PK pre-dose
 - Biomarker assessments
- Leicester Cough Questionnaire and Cough VAS
- Spirometry
- Subject will return the used and unused study drug
- Administer Study Drug

Assessments and procedures performed after dosing include:

- Adverse event assessment

- Vital signs
- Collect blood for the following:
 - PK at 5 minutes (+ 5 minutes) after dosing
 - Spirometry at 30 minutes (\pm 10 minutes) and 1 hour (\pm 10 minutes) after dosing
- Bronchoscopy with BAL and/or BA and deep bronchial brushings after all other Day 14 assessments are complete

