## **8.7. Leicester Cough Questionnaire**

The Leicester Cough Questionnaire (LCQ) is a subject self-report, health related quality of life questionnaire (see [Appendix 14.2](#)) that will be collected per SOA (see [Appendix 14.1](#)). The LCQ consists of three domains where domain scores are equal to the total score from the questions in the domain divided by the number of questions in the domain (domains scores range from 1 to 7):

1. Physical: Questions 1, 2, 3, 9, 10, 11, 14, and 15
2. Psychological: Questions 4, 5, 6, 12, 13, 16, and 17
3. Social: Questions 7, 8, 18, and 19

LCQ total score is equal to the sum of the domain scores (total score range from 3 to 21) with a lower score indicating greater impairment of health status due to cough. The LCQ domain and total scores will be derived for use during analysis. If a response is not provided to a question, the domain score will be calculated as the average of the scores to the answered questions within the domain. If a subject responds to less than 80% of questions in a domain, the LCQ domain score will not be calculated and will be treated as missing during analysis. If it is not possible to calculate all domain scores following this criteria, total score will not be calculated and will be treated as missing during analysis.

Descriptive statistics for observed and change from baseline values will be presented for LCQ domain and total scores by scheduled visit and treatment (active treatments, active treatment total, and pooled placebo) and overall for the Safety Set.

LCQ data will be presented in a listing for the Safety Set.

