## **8.8. Cough Visual Analogue Scale**

The cough VAS is a 100 mm scale (See [Appendix 14.3](#)) on which a subject will be asked to mark between 'no cough' (0 mm) and 'the worst cough severity' (100 mm).

Descriptive statistics for observed and change from baseline values will be presented for cough severity VAS by scheduled visit and treatment (active treatments, active treatment total, and pooled placebo) and overall for the Safety Set.

Cough VAS data will be presented in a listing for the Safety Set.

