## 14.2. Leicester Cough Questionnaire

This questionnaire is designed to assess the impact of cough on various aspects of your life. Read each question carefully and answer by CIRCLING the response that best applies to you. Please answer ALL questions, as honestly as you can.

1. In the last 2 weeks, have you had chest or stomach pains as a result of your cough?

1 All of the time	2 Most of the time	3 A good bit of the time	4 Some of the time	5 A little of the time	6 Hardly any of the time	7 None of the time
----------------------	-----------------------	-----------------------------	-----------------------	---------------------------	-----------------------------	-----------------------

2. In the last 2 weeks, have you been bothered by sputum (phlegm) production when you cough?

1 Every time	2 Most times	3 Several times	4 Some times	5 Occasionally	6 Rarely	7 Never
-----------------	-----------------	--------------------	-----------------	-------------------	-------------	------------

3. In the last 2 weeks, have you been tired because of your cough?

1 All of the time	2 Most of the time	3 A good bit of the time	4 Some of the time	5 A little of the time	6 Hardly any of the time	7 None of the time
----------------------	-----------------------	-----------------------------	-----------------------	---------------------------	-----------------------------	-----------------------

4. In the last 2 weeks, have you felt in control of your cough?

1 None of the time	2 Hardly any of the time	3 A little of the time	4 Some of the time	5 A good bit of the time	6 Most of the time	7 All of the time
-----------------------	-----------------------------	---------------------------	-----------------------	-----------------------------	-----------------------	----------------------

5. How often during the last 2 weeks have you felt embarrassed by your coughing?

1 All of the time	2 Most of the time	3 A good bit of the time	4 Some of the time	5 A little of the time	6 Hardly any of the time	7 None of the time
----------------------	-----------------------	-----------------------------	-----------------------	---------------------------	-----------------------------	-----------------------

6. In the last 2 weeks, my cough has made me feel anxious

1 All of the time	2 Most of the time	3 A good bit of the time	4 Some of the time	5 A little of the time	6 Hardly any of the time	7 None of the time

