### 14.3. Cough Visual Analogue Scale

Please put a cross on the line to indicate the severity of your cough in the past 2 weeks.

Note this scale is 100 mm long.

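### Does the Day 1 baseline for the LCQ and cough VAS, whose 2-week recall can include the baseline bronchoscopy, call for a second Day 14 change measured from Screening?

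*SAP*

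**What the plan says.** SAP 4.1 gives a general rule: "baseline will be defined as the last non-missing evaluation prior to the date and time that the first dose of treatment is taken". Spirometry has its own baseline rule there; the LCQ and the cough VAS do not.

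The collection times are in the protocol:
- Screening (7.1): "Leicester Cough Questionnaire and Cough VAS prior to bronchoscopy".
- Day 1 (7.2.1): "Leicester Cough Questionnaire and Cough VAS" stands among the assessments made before dosing. This score is the baseline unless it is missing, in which case the rule falls back to Screening.
- Day 14 (7.2.5): the cough scales are completed before dosing, and the second procedure comes last: "Bronchoscopy with BAL and/or BA and deep bronchial brushings after all other Day 14 assessments are complete".

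The LCQ items ask about the preceding 2 weeks, for example "In the last 2 weeks, have you had chest or stomach pains as a result of your cough". The VAS does the same: "Please put a cross on the line to indicate the severity of your cough in the past 2 weeks".

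The planned summaries are, for the LCQ (SAP 8.7), "Descriptive statistics for observed and change from baseline values will be presented for LCQ domain and total scores by scheduled visit and treatment", and for the VAS (SAP 8.8), "Descriptive statistics for observed and change from baseline values will be presented for cough severity VAS by scheduled visit and treatment". Both sections also plan listings, and SAP 4 plans listings of all study data by subject. SAP 4 states that no hypothesis is tested.

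**The concern.** The Screening and Day 14 scores are each taken before that visit's bronchoscopy. The Day 1 score is usually taken after one and looks back over it. If a bronchoscopy makes patients cough for a while, the Day 1 score could be worse than the patient's usual state. A later change from Day 1 would then look like improvement.

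That direction is the awkward one for a safety endpoint, because it could mask cough caused by the drug. Protocol 1.1.1.3 reports mild dry cough as the most common TEAE in the three lower-dose multiple-dose cohorts of the earlier study, so readers will look at these scores. A pre-bronchoscopy score exists at Screening, yet no change from it is planned. It is natural to ask for a supportive Screening-to-Day 14 change.

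**Working it through.** The plan states no figure on this point, so there is none to reproduce.

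**1. Day count.** Inputs: bronchoscopy allowed on Days -21 to -1 with no minimum gap before Day 1 (Protocol 7.1), which is 21 days; recall of 14 days; no Day 0 (SAP 4.1).
- Day 1 recall covers Days -14 to -1: 14/21 = 67%.
- Day 14 recall covers Day -1 and Days 1 to 13: 1/21 = 5%. With the visit on Day 13 it is 2/21, on Day 15 it is 0/21.
- Difference: (14 - 1)/21 = 13/21 = 62%.

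These are counts of permitted days and not probabilities. Protocol 3 has the bronchoscopy done in subjects who meet the screening criteria, so it may cluster late in Screening.

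**2. What the extra change would add.** For each subject,

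(Day 14 - Screening) - (Day 14 - Day 1) = Day 1 - Screening.

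The two Day 14 changes differ only by the Screening-to-Day 1 change. Both visits are collection visits for these scales, so with complete data the mean of that difference is the Day 1 mean minus the Screening mean, both in the planned summaries of observed scores. The individual values follow from the listings of about 24 subjects. Only the printed SD, median and range of the paired change are missing.

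**3. Whether it would show a bronchoscopy effect.** Every subject is planned to have the procedure, so no group lacks it. The Screening-to-Day 1 change also contains ordinary variation, earlier illness and stopped supplements: Protocol 4.1.2 excludes febrile illness and supplement use before dosing only within 7 days. A difference would not identify bronchoscopy as the cause, and the absence of one would not exclude it.

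**4. Whether Screening is the cleaner reference.** Let B be the worsening of a score when post-procedure cough lies in its recall, and L the days of cough after the procedure day. Both are assumptions; the documents give neither, and B may be zero. First suppose a score shifts by the full B if any cough day is in its recall, with bronchoscopy days equally likely within each range. Minus means toward improvement.

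| Bronchoscopy days | L | Shift, Day 1 reference | Shift, Screening reference |
|---|---|---|---|
| -21 to -1 | 0 | (1 - 14)/21 = -0.62B | 1/21 = +0.05B |
| -21 to -1 | 3 | (4 - 17)/21 = -0.62B | 4/21 = +0.19B |
| -21 to -15 | 0 | 0 | 0 |
| -7 to -1 | 0 | (1 - 7)/7 = -0.86B | 1/7 = +0.14B |
| -7 to -1 | 3 | (4 - 7)/7 = -0.43B | 4/7 = +0.57B |
| -7 to -1 | 6 | (7 - 7)/7 = 0 | 7/7 = +1.0B |

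Screening is better in some rows and worse in others.

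**5. Whether the two changes bracket the truth.** In the table the two shifts have opposite signs or one or both are zero, which suggests reporting them as a range. That depends on the all-or-none assumption, whereas most LCQ items ask how much of the time. Let the shift instead grow with the number of cough days recalled, with bronchoscopy on Days -3, -2 and -1 and L = 6:
- Cough days in Day 1 recall: 3, 2, 1 (mean 2).
- Cough days in Day 14 recall: 5, 6, 7 (mean 6).
- Shift with Day 1 reference: 6 - 2 = +4 days. With Screening reference: 6 - 0 = +6 days.

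Both lie on the same side, so the pair does not bracket the unshifted change. The Day 1 shift is here toward worsening, so its direction is not fixed either.

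**6. Placebo contrast.** Randomization is on Day 1, after the bronchoscopy, so timing cannot depend on the arm. Within a cohort the expected shift in LTI-03 minus placebo is 0. Chance differences in timing remain. Under equally likely days and L = 0 their SD is sqrt(13/21 x 8/21) x sqrt(1/9 + 1/6) = 0.486 x 0.527 = 0.26B for 9 versus 6 pooled placebo. For 9 versus the cohort's own 3 it is 0.486 x sqrt(1/9 + 1/3) = 0.486 x 0.667 = 0.32B.

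**The case for a change.** The best case for the extra table is that it is cheap and uses data already collected. The SAP already departs from the default baseline for spirometry. Under equally likely timing and short-lived cough, the Screening reference is much less exposed: 0.05B against 0.62B. If B were as large as 2 LCQ points or 15 mm on the VAS (assumed values without a source in the documents), the Day 1-based within-arm change would move by 13/21 x 2 = 1.24 points or 13/21 x 15 = 9.3 mm. Timing noise in the 9-versus-6 contrast would also fall, from 0.26B to sqrt(1/21 x 20/21) x 0.527 = 0.11B.

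The arithmetic stands, and so does the advice to read within-arm cough changes with the bronchoscopy in mind. The step to a needed analysis does not. The gain rests on an unknown B and on a timing pattern that the protocol does not set. If all bronchoscopies fall on Days -14 to -1, the noise is the same for both references (0.14B at L = 0). The Screening score can be up to 3 weeks old and describes the patient less well at the start of dosing.

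One reservation about placebo also stands. Placebo is pooled over two sequential cohorts, so comparing a single cohort with it has an expected shift of 0 only if bronchoscopy timing is alike in both cohorts. The documents do not say whether it is. Either Day 14 change carries this reservation.

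**Conclusion.** The concern does not hold. The day counts are correct, 14 of 21 against 1 of 21, but no rule in the SAP is shown to give a wrong result. The last pre-dose score is a defensible reference for change on treatment, and one baseline serves Days 7, 14 and 21 alike. The effect at issue is B, which the documents do not give and which may be zero. If it is not zero, it touches only a descriptive within-arm change in two safety scales. It does not touch TEAE incidence, which is the primary endpoint, and it does not shift the expected within-cohort difference from placebo.

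A Screening-to-Day 14 change would repeat information that the visit summaries and listings already give, could not attribute a difference to bronchoscopy, and would be the worse reference when bronchoscopies are late and cough lasts. Reporting the two changes as the ends of a range would be unsafe, because the bracketing fails once the effect depends on the number of cough days recalled. What is left is a preference for one more table.

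This conclusion assumes that the Screening and Day 1 scores are largely complete, so that the difference of visit means describes the same subjects, and that the planned listings are produced.
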